7.4 Assessment of Safety

The safety profile of the study drug will be assessed through the recording, reporting, and analyzing of baseline medical conditions, AEs, physical examination findings including vital signs and laboratory tests.

Comprehensive assessment of any apparent toxicity experienced by the subject will be performed throughout the course of the trial, from the time of the subject's signature of informed consent. Trial site personnel will report any AE, whether observed by the Investigator or reported by the subject (see Section 7.4.1.2, "Methods of Recording and Assessing Adverse Events"). Given the intended mechanism of action of the study drug, particular attention will be given to AEs that may

follow the enhanced T-cell activation, such as dermatitis, colitis, hepatitis, uveitis, or other immune-related reactions. Ophthalmologic examinations should be performed, when clinically indicated, for signs or symptoms of uveitis.

The reporting period for AEs is described in Section 7.4.1.3.

The safety assessments will be performed according to the Schedule of Assessments (refer to Appendix I).

7.4.1 Adverse Events

7.4.1.1 Adverse Event Definitions

Adverse event

An AE is any untoward medical occurrence in a subject or clinical investigation subject administered a pharmaceutical product, which does not necessarily have a causal relationship with this treatment. An AE can therefore be any unfavorable and unintended sign (including an abnormal laboratory finding), symptom, or disease temporally associated with the use of a medicinal product, whether or not considered related to the medicinal product.

In cases of surgical or diagnostic procedures, the condition/illness leading to such a procedure is considered as the AE rather than the procedure itself.

The Investigator is required to grade the severity/intensity of each AE.

Investigators will reference the NCI-CTCAE v 4.0 (publication date: 28 May 2009). This is a descriptive terminology that can be used for AE reporting.

A general grading (severity / intensity) scale is provided at the beginning of the referenced document, and specific event grades are also provided.

If a particular AE's severity / intensity is not specifically graded by the guidance document, the Investigator is to revert to the general NCI-CTCAE definitions of Grade 1 through Grade 5 and use his or her best medical judgment.

The 5 general grades are:

Grade 1: Mild

Grade 2: Moderate

Grade 3: Severe

Grade 4: Life-threatening or disabling

Grade 5: Death related to AE

According to the Sponsor's convention, if a severity/intensity of Grade 4 or 5 is applied to an AE, then the Investigator must also report the event as a serious adverse event (SAE; see definition below) as per Section 7.4.1.4; however, a laboratory abnormality with a severity/intensity of Grade 4, such as anemia or neutropenia, is considered serious only if the condition meets one of the serious criteria described below.

In the case of death, the primary cause of death (or the event leading to death) should be recorded and reported as an SAE. "Fatal" will be recorded as the outcome of this respective event; death will not be recorded as separate event. Only if no cause of death can be reported (for example, sudden death, unexplained death), the death per se might be reported as an SAE.

Investigators must also systematically assess the causal relationship of AEs to the study drug using the following definitions. Decisive factors for the assessment of causal relationship of an AE to avelumab include, but may not be limited to, temporal relationship between the AE and avelumab, known side effects of avelumab, medical history, concomitant medication, course of the underlying disease, trial procedures.

Not related: Not reasonably suspected to be related to the study drug. The AE could not medically (pharmacologically/clinically) be attributed to the study drug under trial in this clinical trial protocol. A reasonable alternative explanation must be available.

Related: Suspected related to the study drug. The AE could medically (pharmacologically/clinically) be attributed to the study drug under trial in this clinical trial protocol.

Abnormal laboratory findings and other abnormal investigational findings

Abnormal laboratory findings and other abnormal investigational findings (for example, on an ECG trace) of Grade < 3 should not be reported as AEs unless they are associated with clinical signs and symptoms, lead to treatment discontinuation or are considered otherwise medically important by the Investigator. If an abnormality of Grade < 3 fulfills these criteria, the identified medical condition (for example, anemia, increased ALT) must be reported as the AE rather than the abnormal value itself.

Adverse Drug Reaction (ADR)

ADRs are defined in this trial as any AEs suspected to be related to avelumab by the Investigator and / or Sponsor.

Serious adverse event (SAE)

A SAE is any untoward medical occurrence that at any dose:

- Results in death,
- Is life-threatening,

NOTE: The term “life-threatening” in this definition refers to an event in which the subject is at risk of death at the time of the event; it does not refer to an event that hypothetically might cause death if it were more severe.

- requires inpatient hospitalization or prolongation of existing hospitalization,
- results in persistent or significant disability / incapacity,
- is a congenital anomaly / birth defect, or
- is otherwise considered as medically important.

Important medical events that may not result in death, be life-threatening, or require hospitalization may be considered as SAEs when, based upon appropriate medical judgment, they may jeopardize the subject or may require medical or surgical intervention to prevent one of the outcomes listed in this definition. Examples of such events include allergic bronchospasm requiring intensive treatment in an emergency room or at home, blood dyscrasias or convulsions that do not result in inpatient hospitalization, or the development of drug dependency or drug abuse.

For the purposes of reporting, any suspected transmission of an infectious agent via a study drug is also considered a SAE and all such cases should be reported in an expedited manner as described in Section 7.4.1.4.

Events that do not meet the definition of an SAE

Elective hospitalizations to administer, or to simplify trial treatment or trial procedures (for example, an overnight stay to facilitate chemotherapy and related hydration therapy application) are not considered as SAEs; however, all events leading to unplanned hospitalizations or unplanned prolongation of an elective hospitalization (for example, undesirable effects of any administered treatment) must be documented and reported as SAEs.

Events not to be considered as AEs / SAEs

Medical conditions present at the initial trial visit that do not worsen in severity or frequency during the trial are defined as Baseline Medical Conditions, and are NOT to be considered AEs.

AE / SAEs observed in association with disease progression

Disease progression recorded in the course of efficacy assessments only, but without any adverse signs or symptoms should not be reported as adverse events.

However, if adverse signs and symptoms occur in association with disease progression then these should be recorded as AEs or reported as SAEs, if they meet criteria for seriousness.

Predefined AEs of special interest for safety monitoring

Any AE that is suspicious to be a potential irAE will be considered AEs of special interest (AESI).

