3.4.1.1 Safety Results

Expansion: All adverse events

CCI

CCI

CCI

[figure not shown]

CCI

CCI

CCI

CCI

CCI

Blood chemistry

A considerable proportion of subjects (up to over 60% for some measure expansion cohort experienced blood chemistry laboratory abnormalities; how abnormalities were relatively mild (Grade 1 or 2). Grade 3 or 4 blood chem occurred less frequently. The following Grade 3 or 4 abnormalities were ob subjects: GGT increased, which was reported in 87 subjects (18.1%) treated in the dose expansion phase, hyponatremia (32 subjects, 6.7%), and AST increased (30 subjects, 6.3%).

CCI

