5.1.4.2 Adverse Drug Reactions Requiring Treatment Discontinuation or Modifications

The following ADRs require permanent treatment discontinuation of avelumab:

Any Grade 4 ADRs require treatment discontinuation with avelumab except for single laboratory values out of normal range that are unlikely related to trial treatment as assessed by the Investigator, do not have any clinical correlate, and resolve within 7 days with adequate medical management.

Any Grade 3 ADRs require treatment discontinuation with avelumab except for any of the following:

- Transient (≤ 6 hours) Grade 3 flu-like symptoms or fever, which is controlled with medical management
- Transient (≤ 24 hours) Grade 3 fatigue, local reactions, headache, nausea, emesis that resolves to Grade ≤ 1

- Single laboratory values out of normal range (excluding Grade ≥ 3 liver function test increase) that are unlikely related to trial treatment according to the Investigator, do not have any clinical correlate, and resolve to Grade ≤ 1 within 7 days with adequate medical management
- Tumor flare phenomenon defined as local pain, irritation, or rash localized at sites of known or suspected tumor
- Change in Eastern Cooperative Oncology Group Performance Status (ECOG PS) to ≥ 3 that does not resolve to ≤ 2 within 14 days (infusions should not be given on the following cycle, if the ECOG PS is ≥ 3 on the day of study drug administration)
- Asymptomatic Grade ≥ 3 lipase or amylase elevation not associated with clinical manifestations of pancreatitis. Medical Monitor must be consulted for such lipase and amylase abnormalities.

Any Grade 2 ADR should be managed as follows:

- Infusion should not be given in case of ongoing Grade 2 ADR on the day of study treatment administration.
- Treatment can be resumed according to the original schedule once the ADR has resolved to Grade ≤ 1 . Up to 2 subsequent study drug may be omitted. If more than 2 doses are skipped, treatment may be resumed after consultation with the Medical Monitor.

Infusion-related reactions, hypersensitivity reactions (Grades 1 to 4), tumor lysis syndrome, and irAEs should be handled according to guidelines in Sections 6.5.4.1, 6.5.4.2, 6.5.4.3, and 6.5.4.4, respectively.

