
Grade 3 to 4
 
Grade 3: Severe new symptoms; New / worsening hypoxia;
 
Grade 4: life-threatening
	
Discontinue avelumab therapy
 
Hospitalize
 
Pulmonary and Infectious Disease consults
 
1.0 to 2.0 mg/kg/day prednisone or equivalent
 
Add prophylactic antibiotics for opportunistic infections
 
Consider bronchoscopy, lung biopsy
	
If improves to Grade \leq 1:
 
Taper steroids over at least 1 month
 
If not improving after 48 hours or worsening:
 
Add additional immunosuppression (for example, infliximab, cyclophosphamide, IV immunoglobulin, or mycophenolate mofetil)

Hepatic irAEs		
Grade of Liver Test Elevation (NCI-CTCAE v4)	Management	Follow-up

Grade 1
 
Grade 1 AST or ALT $>$ ULN to $3.0 \times$ ULN and / or total bilirubin $>$ ULN to $1.5 \times$ ULN
	
Continue avelumab therapy
	
Continue liver function monitoring
 
If worsens:
 
Treat as Grade 2 or 3 to 4

Grade 2
 
AST or ALT $>$ 3.0 to $\leq 5 \times$ ULN and / or total bilirubin $>$ 1.5 to $\leq 3 \times$ ULN
	
Delay avelumab therapy
 
Increase frequency of monitoring to every 3 days
	
If returns to Grade \leq 1:
 
Resume routine monitoring, resume avelumab therapy
 
If elevations persist $>$ 5 to 7 days or worsen:
 
Treat as Grade 3 to 4

Grade 3 to 4
 
AST or ALT $>$ $5 \times$ ULN and / or total bilirubin $>$ $3 \times$ ULN
	
Discontinue avelumab therapy
 
Increase frequency of monitoring to every 1 to 2 days
 
1.0 to 2.0 mg/kg/day prednisone or equivalent
 
Add prophylactic antibiotics for opportunistic infections
 
Consult gastroenterologist / hepatologist
 
Consider obtaining MRI/CT scan of liver and liver biopsy if clinically warranted (for trial sites in Germany, only MRI is to be used)
	
If returns to Grade \leq 1:
 
Taper steroids over at least 1 month
 
If does not improve in $>$ 3 to 5 days, worsens or rebounds:
 
Add mycophenolate mofetil 1 gram (g) twice daily
 
If no response within an additional 3 to 5 days, consider other immunosuppressants per local guidelines

Renal irAEs		
Grade of Creatinine Increased (NCI-CTCAE v4)	Management	Follow-up
Grade 1 Creatinine increased > ULN to 1.5 × ULN	Continue avelumab therapy	Continue renal function monitoring If worsens: Treat as Grade 2 to 3 or 4.

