Grade 2 to 3 Creatinine increased > 1.5 and ≤ 6 × ULN	Withhold avelumab therapy Increase frequency of monitoring to every 3 days 1.0 to 2.0 mg/kg/day prednisone or equivalent. Add prophylactic antibiotics for opportunistic infections Consider renal biopsy	If returns to Grade ≤ 1: Taper steroids over at least 1 month, and resume avelumab therapy following steroids taper. If worsens: Treat as Grade 4.
Grade 4 Creatinine increased > 6 × ULN	Permanently discontinue avelumab therapy Monitor creatinine daily 1.0 to 2.0 mg/kg/day prednisone or equivalent. Add prophylactic antibiotics for opportunistic infections Consider renal biopsy Nephrology consult	If returns to Grade ≤ 1: Taper steroids over at least 1 month.
Endocrine irAEs		
Endocrine Disorder	Management	Follow-up
Grade 1 or Grade 2 endocrinopathies (hypothyroidism, hyperthyroidism, adrenal insufficiency, type I diabetes mellitus)	Continue avelumab therapy Endocrinology consult if needed Start thyroid hormone replacement therapy (for hypothyroidism), anti-thyroid treatment (for hyperthyroidism), corticosteroids (for adrenal insufficiency) or insulin (for Type I diabetes mellitus) as appropriate. Rule-out secondary endocrinopathies (i.e. hypopituitarism / hypophysitis)	Continue hormone replacement/suppression and monitoring of endocrine function as appropriate.

Grade 3 or Grade 4 endocrinopathies (hypothyroidism, hyperthyroidism, adrenal insufficiency, type 1 diabetes mellitus)
	
Withhold avelumab therapy Consider hospitalization Endocrinology consult
 
Start thyroid hormone replacement therapy (for hypothyroidism), anti-thyroid treatment (for hyperthyroidism), corticosteroids (for adrenal insufficiency) or insulin (for type 1 diabetes mellitus) as appropriate.
 
Rule-out secondary endocrinopathies (i.e. hypopituitarism / hypophysitis)
	
Resume avelumab once symptoms and/or laboratory tests improve to Grade \leq 1 (with or without hormone replacement/suppression).
 
Continue hormone replacement/suppression and monitoring of endocrine function as appropriate.

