Appendix II Description of criteria for Adverse Events of Special Interest

A two-level approach is pursued to analyze potential immune-related adverse events (AEs):

1. A MedDRA Preferred Term (PT) query is used for each event category (i.e., immune-mediated rash, colitis, pneumonitis, hepatitis, nephritis and renal dysfunction, endocrinopathies and other immune-mediated adverse reactions).
2. AEs identified by the MedDRA PT queries will then be medically reviewed using pre-defined case definitions for immune-mediated adverse reactions.

Level 1:

To identify potentially immune-mediated AEs, MedDRA PT queries will be used to search for AEs of interest in the clinical database. The relevant event categories and corresponding MedDRA PT queries are documented in a version-controlled repository maintained by the Sponsor and finalized for analysis of the current study data prior to DB lock.

The respective MedDRA PT queries will be used to identify AEs reported in the current study that are potentially immune-mediated events.

Level 2:

In a second level (medical review), the potential immune-mediated AEs identified from the search performed at Level 1, will be reviewed by qualified medical personnel to determine whether the AE meets the criteria (case definition) for an immune-mediated adverse reaction based on the following algorithm:

Table 13 Algorithm for immune-related adverse reactions

| Criteria | Description |
|---|--|
| Onset | AE onset after 1st avelumab administration until up to 90 days after last dose |
| Duration | AE does not spontaneously resolve (i.e., without corticosteroids/ immunosuppressant treatment) within 7 days after onset |
| Immunosuppressive therapy | AE treated with corticosteroid or other immunosuppressant therapy. For endocrinopathies only: AE required hormone replacement* and /or (corticosteroid or other immunosuppressive therapy) |
| Etiology | No other clear etiology or Histopathology/biopsy consistent with immune-mediated event |
| All criteria listed in the left column need to be fulfilled for an event to meet the case definition of immune-mediated reaction. | |
| *Hormone replacement will be evaluated for specific endocrinopathy disorders only as follows: 
 • Thyroid disorders (HLT): Thyroid therapy (ATC codes (H03A, H03B)) • Diabetes mellitus (including hyperglycemia): Insulin (ATC code A10A) | |

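### Dose holds and steroid treatment do not trigger AE reporting for laboratory findings below Grade 3, so silent Grade 2 liver and kidney events that changed treatment can be missing from the AE tables

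*Protocol*

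**What the plan says.** Protocol Section 7.4.1.1, on abnormal laboratory findings, states that those "of Grade < 3 should not be reported as AEs unless they are associated with clinical signs and symptoms, lead to treatment discontinuation". A further exception leaves it to the investigator to report a finding that he or she regards as important on other medical grounds. When a Grade 1 or 2 finding meets one of these conditions, the underlying medical condition has to be reported as the AE; a raised ALT is one of the examples given.

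Table 5 in Protocol Section 6.5.4.4 describes hepatic and renal irAEs by laboratory value alone. For Grade 2 ALT, AST or bilirubin the action is "Delay avelumab therapy", with closer monitoring and no steroid at that step. For Grade 2 to 3 creatinine it is "Withhold avelumab therapy Increase frequency of monitoring to every 3 days 1.0 to 2.0 mg/kg/day prednisone or equivalent". Protocol Section 5.1.4.2 adds a general rule: "Infusion should not be given in case of ongoing Grade 2 ADR on the day of study treatment administration".

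The Part A SAP (Section 17.1) identifies irAEs from a list of MedDRA preferred terms. The Part B SAP (Appendix II) runs preferred-term queries, and "AEs identified by the MedDRA PT queries will then be medically reviewed using pre-defined case definitions for immune-mediated adverse reactions". Both SAPs take relatedness from the AE page of the eCRF.

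**The concern.** The reporting rule and the management table use different thresholds. Table 5 treats certain Grade 2 laboratory results as serious enough to interrupt treatment and, for creatinine, to start a systemic steroid. Section 7.4.1.1 starts from non-reporting at the same grade, and neither of those actions lifts an event out of that default. Whether a symptom-free event is recorded then depends on how each investigator reads medical importance.

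The occurrence and severity of treatment-related AEs is a secondary endpoint in both parts. Protocol Section 3.6 names irAEs as a primary risk, and Section 5.1 gives Part B a confirmatory role for some approvals. Counts of liver and kidney events could be too low and could differ between sites for reasons unrelated to the drug.

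**Working it through.** The plan gives no figure to reproduce, so the check follows two asymptomatic Grade 2 events through the text.

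| Step | Creatinine, Grade 2 | ALT, AST or bilirubin, Grade 2, resolving after a delay |
|---|---|---|
| Action in Table 5 | Avelumab withheld, prednisone given | Avelumab delayed, no steroid |
| Symptom trigger | Not met | Not met |
| Discontinuation trigger | Not met: a temporary hold, which Table 5 words differently from discontinuation | Not met, for the same reason |
| Medical-importance trigger | Investigator's judgement | Investigator's judgement |
| If not judged important: AE and related-AE tables, both parts | Missing | Missing |
| Part A irAE table | Missing | Missing |
| Part B irAE table | Missing, although the event could have qualified | Would not qualify even if reported |

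The last row follows from Table 13 of the Part B SAP. An irAE there must have been treated with a steroid or other immunosuppressant (hormone replacement also counts for endocrine events) and must not have resolved on its own within 7 days. A short liver elevation managed by delay alone fails this. A liver elevation that lasts beyond 5 to 7 days, or worsens, moves to the Grade 3 to 4 row of Table 5, where avelumab is discontinued; it then meets an existing reporting trigger. That leaves mainly the renal event exposed in the Part B irAE table.

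Nothing later in the chain recovers an unreported event as an AE:
- An ADR is defined in Section 7.4.1.1 as an AE suspected to be related, so the Grade 2 ADR rule in Section 5.1.4.2 presupposes an AE.
- The special-interest category in Section 7.4.1.1 likewise begins from an AE.
- The preferred-term searches in both SAPs can find only coded AEs.

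The weight of one missing subject:
- Part B: 1/112 = 0.0089, or 0.9 percentage points.
- Part A, with the 88 treated subjects stated in Section 7 of its SAP: 1/88 = 0.0114, or 1.1 percentage points.

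**The case against.** The strongest reply is that investigators will report these events anyway. An investigator who withholds avelumab and starts prednisone would find it hard to call the creatinine rise unimportant. The raised-ALT example shows that Grade 1 and 2 reports are expected. Other text leans the same way: Section 7.4 asks for particular attention to hepatitis, Section 7.4.1.2 has unfavourable changes recorded as AEs, and Section 7.4.4 does the same for new or worsening conditions. Table 5 is a management table and does not declare every Grade 2 value an irAE. The eCRF Completion Guidelines, which are not among the documents, may say more. All this stands as a reason to expect that many such events are reported. It does not remove the problem: Section 7.4.1.1 is the specific rule, its exception is discretionary, and nothing links that exception to Table 5.

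A second reply is that the information is captured elsewhere. Concomitant drugs are recorded with their indication, dose delays are summarised, laboratory grades and shifts are tabulated, and liver values are listed for every subject with ALT or AST at or above 3 × ULN. A reader might infer from the reporting rule that unreported events are lost for good; the documents do not support that. What is missing without an AE record is the relatedness assessment and the irAE classification, and no planned table joins a Grade 2 value to a dose hold or to steroid use.

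A reader might also infer that hepatic irAE rates in Part B are understated. The Part B case definition does not support this for short, untreated liver elevations.

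**Conclusion.** The point holds as a gap in the reporting rule. Asymptomatic Grade 2 events that changed treatment can be missing, at the discretion of the site. Liver and kidney events are exposed in the AE and related-AE tables of both parts and in the Part A irAE table; in the Part B irAE table the exposure is mainly renal. For the irAE tables this assumes that the sponsor's preferred-term lists, which are not in the documents, include the relevant liver and creatinine terms.

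The size cannot be estimated. It may be tempting to use the Phase I statement in Protocol Section 3.4.1.1 that, for some measures, over 60% of subjects had blood chemistry abnormalities, mostly Grade 1 or 2. That figure covers chemistry measures in general and pools the two grades, while Table 5 continues avelumab at Grade 1 for both liver and kidney, so it says nothing about how often this gap occurs. The documents support the statement that counts can be too low. They do not show that counts are too low, or by how much.

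**What to change.** In Protocol Section 7.4.1.1, add to the conditions under which a finding below Grade 3 is reported: *lead to a delay, withholding or interruption of avelumab, or to treatment with corticosteroids, other immunosuppressants or hormone replacement*.

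For data already collected, add a medical-review listing of every on-treatment Grade 2 ALT, AST, bilirubin or creatinine value that is accompanied by a dose delay or a new systemic steroid but has no AE record, and query the site. For Part A, whose main results Protocol Section 10.6.2 cites as published, only this listing can still help.

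The cost is one protocol sentence and one data-review listing, with some additional AE records and a slightly less favourable AE table. The change concerns reporting only and leaves the management rules in Table 5 unchanged.
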